## GLOSSARY OF ABBREVIATIONS

BASEC	Business Administration System for Ethical Committees
CRF	Case report form
FOPH	Federal Office of Public Health

*HRA*      *Human Research Act*  
*HRO*      *Ordinance on Human*

## 1 BACKGROUND AND PROJECT RATIONALE

Hyponatremia, defined as a serum sodium level below <136 mmol/L, is an often encountered disorder in hospitalized patients, with a prevalence of about 10% of patients presenting to the emergency department [1-3]. While the excess mortality seen in hyponatremic patients has long been attributed to the severity of the underlying disease, as it is potentially true in heart failure and other conditions, recent studies have shown that hyponatremia itself has a negative impact on patient outcomes, irrespective of the type and severity of the underlying disease [4-8]. Even a slight decrease of the serum sodium level was shown to be independently associated with adverse outcomes, such as mortality or increase in length of ICU/hospital stay [6, 8]. To date, the mechanisms leading to worse prognosis in patients with hyponatremia remain largely unknown. Evidence suggests that patients with hyponatremia may be more prone to falls resulting in an increased incidence of fractures in such patients [9-11]. In addition, chronic hyponatremia may be associated with decreased bone density and therefore a higher risk of fractures [12-14]. A small recent study showed an association between hyponatremia and psychomotor disturbances, such as attention deficits and gait difficulties [15].

The above mentioned effects of acute hyponatremia might be explained by cellular hyperhydration, the same mechanism that also leads to cerebral edema [3]. In chronic hyponatremia, compensatory mechanisms, such as a shift of organic and inorganic osmotically active substances from the intracellular to the extracellular space, have already occurred and decrease cellular edema [3, 16]. However, resting membrane potential is a function of sodium and potassium concentrations. Thus, hyponatremia might directly influence nerve conduction velocity and muscle strength.

In summary, limited evidence suggests that hyponatremia appears to influence neurologic functions leading to attention deficits, gait disturbances, and a higher risk of fractures. Given the low quality of existing data, the association between hyponatremia and these adverse outcomes must be further examined, preferably in an adequately powered prospective study.

### *Preliminary studies*

- I. In a large study including multiple intensive care units in Austria, our group demonstrated that even mild decreases in serum sodium (i.e., serum sodium 130 – 135 mmol/L) were associated with an increased mortality, adjusting for age, admission diagnosis, and severity of illness as measured by the Severe Acute Physiology Score (SAPS) II [6].
- II. Another study by our group showed that hyponatremia at the time of hospital admission is often not noticed and consequently, not or inadequately treated during hospitalization [11].
- V. Refardt and coworkers demonstrated an increase in cognitive function but could not show an improvement in gait after correction of sodium levels [29].
- VI. Vanderghenst and coworkers could show no improvement in strength after correction in moderate hyponatremia, but could show impaired nerve conduction with significant improvement through correction in severe hyponatremia [PMID 26835607].
- VII. Albabtain and coworkers found a correlation between hyponatremia and impaired cognitive function in patients with heart failure but none for impaired mobility [PMID 27988787].
- VIII. Murthy and coworkers did a metaanalysis regarding bone density and fractures in hyponatremia, showing a significantly increased risk for osteoporosis, all-site fractures, mortality and duration of hospital stay in Patients with hyponatremia [PMID 30720342].
- IX. Usala and coworkers conducted a metaanalysis regarding osteoporosis and prevalence of fractures in diabetic patients with hyponatremia, showing a significantly increased risk for osteoporosis and fractures in hyponatremia [PMID 30746503]
- X. Corona and coworkers showed in a metanalysis an increased risk for fractures even in mild hyponatremia [PMID 29920727].

## 2 PROJECT OBJECTIVES AND DESIGN

### 2.1 Hypothesis and primary objective

Our broad objective is to prospectively examine in a prospective study whether an association exists between hyponatremia and psychomotor deficits. The specific aims are:

- A) To measure muscle strength by use of a dynamometer in patients presenting with moderate to severe hyponatremia (serum sodium  $\leq 125$  mmol/L) at the emergency department before and after correction of hyponatremia (serum sodium  $\geq 135$  mmol/L).
- B) To test for balance and gait disorders before and after correction of hyponatremia
- C) To investigate whether presence of hyponatremia is associated with cognitive impairment that is reversible after correction of serum sodium.

Our hypothesis is that hyponatremia is associated with reduced muscle strength, impaired balance, and cognitive impairment, and that the correction of the serum sodium will lead to an improvement of these parameters.

### 2.2 Primary and secondary endpoints

- A) Muscle strength in pounds and kilogram before and after correction of hyponatremia.
- B) Results for the Tinetti performance-oriented mobility assessment (POMA) to evaluate static and dynamic balance abilities during and after correction of hyponatremia.
- C) Results for the Montreal Cognitive Assessment (MOCA) test to assess mild cognitive impairment before and after correction of hyponatremia.

Muscle strength at handgrip will be measured at time of presentation at our clinic with a serum sodium  $\leq 125$  mmol/L and 24 to 48 hours after correction of hyponatremia at a serum sodium  $\geq 135$  mmol/L using the Jamar® hydraulic hand dynamometer, Lafayette Instrument, Lafayette, IN, USA. Strength will be measured in pounds and kilograms thrice at baseline and after correction of hyponatremia, respectively. The best result of each test will be used for the analysis. The test will be conducted by either Drs. [name] or [name].

The Tinetti POMA, a simple, easily administered test, will be used to measure patients' gait and balance taking about 10 to 15 minutes [19]. Scoring of the Tinetti Assessment Tool is done on a three point ordinal scale with a range of 0 to 2. A score of 0 represents the most severe impairment, while a 2 would represent patient independence. The individual scores are then combined to form three measures; an overall gait assessment score, an overall balance assessment score, and a gait and balance score. The test has been validated in several studies and found to be a useful screening tool for gait instabilities and prediction of falls [20-22]. The Tinetti POMA form is shown in the Appendix. The test will be performed at baseline and 24 to 48 hours after correction of hyponatremia. The test will be conducted by either Drs. [name] and [name].

The MOCA is a 30-point test administered in about 10 minutes designed to identify mild cognitive impairment [23]. The test is validated for a large variety of diseases ranging from frontotemporal dementia to HIV or chronic obstructive pulmonary disease [24-27]. The MOCA form is shown in the Appendix. The test will be performed at baseline and 24 to 48 hours after correction of hyponatremia. The test will be conducted by either Drs. [name] and [name].

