##### b.) Serum sodium measurements

Measurements of serum sodium will be performed through the Center for Laboratory Medicine of the General Hospital Solothurn. Sodium determination will be performed by use of ion-selective electrode using the ICT (Na+, K+, Cl) Sample Diluent Kit, Abbott Laboratories, Chicago, IL, USA. Additionally, serum osmolality, potassium, magnesium, calcium, creatinine, albumin and hemoglobin as well as urine osmolality, sodium, potassium, creatinine and urea will be measured. All of these parameters are standard measurements in case of a severe electrolyte disorder and are part of clinical practice in the care for patients with electrolyte disorders. All laboratory parameters will be measured at baseline and after correction of serum sodium. In order to avoid multiple blood drawings for the patient the parameters mentioned above will be reordered from blood already taken for serum sodium determination.

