##### c.) Physical and cognitive measurements

Afterwards muscle strength, Tinetti score and MOCA score will be measured. Upon correction of hyponatremia these measurements will be repeated. The study is then completed for the individual participant.

See also Appendix 1.

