## 4 STATISTICS AND METHODOLOGY

### 4.1. Statistical analysis plan

Data will be presented as means and standard deviation or medians and interquartile range as appropriate. Wilcoxon signed ranked tests will be used to compare results on muscle strength, Tinetti score and MOCA scores, since those are not normally distributed and samples will be dependent since every patient serves as his own control. A p-value of  $\leq 0.05$  will be considered statistically significant. Statistics will be calculated using IBM SPSS Statistics 25, IBM, Armonk, New York, USA.

Based on general Patient count and prevalence of Hyponatremia, the enrollment of the sample size of 50 patients seems realistic in a 12-month period, starting on 01 June 2019.

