## Appendix 1: Schedule of assessments

Time	0	Corrected sodium
Visit	Screening/1 st visit	2 nd visit
oral and written Information	+	
Written consent	+	
check inclusion-/ exclusion criteria	+	
Medical history	+	
Participant Characteristics	+	
Serum sodium measurements	+	+
MOCA	+	+
Tinetti Assessment	+	+
Grip Strength	+	+

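### Does the protocol leave the time of the post-correction retest undefined?

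*Protocol*

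**What the plan says.** The retest is described in four places in the protocol.

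- **Section 2.2 (endpoints).** Grip strength is repeated "24 to 48 hours after correction of hyponatremia at a serum sodium" of at least 135 mmol/L. The Tinetti and MOCA paragraphs each carry the sentence "The test will be performed at baseline and 24 to 48 hours after correction of hyponatremia".
- **Section 3.3 b (laboratory).** "All laboratory parameters will be measured at baseline and after correction of serum sodium". No hours are given.
- **Section 3.3 c (physical and cognitive measurements).** "Upon correction of hyponatremia these measurements will be repeated. The study is then completed for the individual participant". It then refers the reader to Appendix 1.
- **Appendix 1 (schedule).** The time row reads 0 for the first visit and "Corrected sodium" for the second. The second-visit column holds serum sodium, MOCA, Tinetti and grip strength.

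Section 4.1 compares the two occasions with Wilcoxon signed-rank tests, on the ground that "samples will be dependent since every patient serves as his own control".

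Two smaller wordings belong to the same topic. Section 1 has hyponatremia "defined as a serum sodium level below <136 mmol/L", while sections 2.1 and 2.2 start the corrected state at 135 mmol/L. Endpoint B in section 2.2 speaks of using the Tinetti test to "evaluate static and dynamic balance abilities during and after correction of hyponatremia", while Aim B in section 2.1 has before and after.

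**The concern.** The retest is one half of every pair, for all three endpoints. Read literally, section 2.2 requires a wait of at least 24 hours after correction, whereas section 3.3 c seems to place the retest at the moment of correction and then ends participation. The procedural text sends the reader to Appendix 1, where the window is also missing, so someone working only from section 3.3 and the schedule would not meet the 24 to 48 hour rule.

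If some patients were retested at once and others one or two days later, the paired differences would mix different amounts of recovery and different retest intervals. A reader could not say which contrast had been estimated. The Tinetti and MOCA paragraphs also give no sodium value for the retest, although the grip-strength sentence does.

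**Working it through.** No formula applies, because the point touches no sample size, power or error rate. The check sets the statements side by side.

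**1. Clock times for the retest.**

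| Place | Stated time | Against 24 to 48 h |
|---|---|---|
| 2.2, grip strength | 24 to 48 h after correction | same |
| 2.2, Tinetti | 24 to 48 h after correction | same |
| 2.2, MOCA | 24 to 48 h after correction | same |
| 3.3 b, laboratory | after correction | compatible, less specific |
| 3.3 c, all three tests | upon correction | compatible or earlier, depending on reading |
| Appendix 1, second visit | label only | compatible, less specific |

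One window is stated, three times and identically. No other number appears. Section 3.3 b and Appendix 1 do not contradict it, since a visit 24 to 48 hours after correction is still a visit after correction. Section 3.3 c is the only possible conflict.

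**2. What *upon* means in this document.** Section 5.6 has the Ethics Committee notified upon termination of the project and allows 90 days for it. There the word means following, with the interval given separately. Section 3.3 c can be read the same way, with section 2.2 supplying the interval. Section 2.2 also shortens its own wording: the sentence after the grip-strength window says the measurements are taken at baseline and after correction, without repeating the hours.

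**3. Size under each reading.**

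- *Upon* as following: discrepancy 0 hours.
- *Upon* as at that moment: the retest falls 24 to 48 hours earlier than section 2.2 asks.
- Scope under either reading: 3 of 3 endpoints and all 50 planned patients (section 3.1). This counts who is covered by both wordings and does not measure harm. The protocol has no data on recovery or practice effects over one to two days, so an effect on the scores cannot be computed.

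**4. The sodium value at retest.** A value is given in 1 of the 3 test paragraphs of section 2.2 (grip strength). Aim A in section 2.1 already defines correction as a sodium of at least 135 mmol/L, and the Tinetti and MOCA paragraphs use the same term. Appendix 1 schedules serum sodium at the same second visit as all three tests.

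**5. The two smaller wordings.** A sodium of 135 mmol/L satisfies both the background definition (below 136) and the corrected state (135 or above). The states actually compared are at most 125 and at least 135 mmol/L, which lie at least 135 − 125 = 10 mmol/L apart, so no measurement can fall in both. The background figure selects no patient and triggers no test. For endpoint B, Aim B, the Tinetti paragraph and Appendix 1 all put the first test before correction or at baseline, so *during* is a slip of wording and no baseline is missing.

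**The case for a change.** The best argument for requiring a change is practical. Section 3.3 and the schedule are the pages used at the bedside, neither carries the window, and neither points back to section 2.2. Nor is the sodium sample named from which the 24 to 48 hours are counted. Sections 3.3 b and 6.1 rely on blood already drawn for routine care. If the second-visit sodium is the sample that first showed correction, tests one or two days later may have no sodium value of their own. The protocol does not mention recording test times, so a mixture of immediate and delayed retests might be hard to disentangle afterwards, while aligning the wording would cost almost nothing.

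Part of this stands. Section 3.3 c is loosely worded, and the sample that starts the clock is left to be understood. The rest is weaker. The study has one centre, and section 2.2 assigns each test to two named doctors, so it is unlikely that different staff would follow different sections. The case report form is not among the documents, so the absence of a date and time field cannot be shown. The interval from baseline to retest depends first on how long correction takes, which varies between patients under any wording. A low cost of editing does not show that the present text leads to a wrong analysis.

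**Conclusion.** No change to the plan follows. The protocol states one retest window, 24 to 48 hours after correction, for all three tests; the other places abbreviate it. At most one word in section 3.3 c can be read against it, giving a discrepancy of nil on one reading and of 24 to 48 hours on the other. No direction or size of bias follows from the documents.

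This rests on two assumptions: that the section which specifies the endpoints governs over a shorter procedural summary, and that the two designated doctors test according to it. Under those assumptions the paired comparison in section 4.1 is well defined as written, and repeating the window elsewhere would not alter any estimate or test. The overlap at 135 mmol/L and the word *during* in endpoint B are clerical and have no effect on who is measured or when.

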#### 3.2 Recruitment, screening and informed consent procedure

If a serum sodium of 125 mmol/L is detected in a blood sample sent from the Department of Emergency Medicine or General Internal Medicine, the Center for Laboratory Medicine will notify the study team (Drs. [name] and [name]) responsible for patient enrollment using a dedicated pager. Then, a member of the study team will approach potential participants, inform them about the study goals and procedures, obtain informed consent, and enroll them into the study. Patients enrolled in the Department of Emergency Medicine needing hospitalization will primarily be hospitalized in the Department of General Internal Medicine, unless hospitalization at specialist ward is indicated.

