### **7 QUALITY CONTROL AND DATA PROTECTION**

#### **7.1 Quality measures**

All data handling will be undertaken directly by the investigators. For quality assurance the Ethics Committee may visit the research sites. Direct access to the source data and all project related files and documents must be granted on such occasions.

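### Unmasked study doctors give every test at both visits and nothing withholds visit 1 scores, so rater expectation could mimic part of the predicted gain, by an unknown amount

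*Protocol*

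**What the plan says.** **Who tests.** Protocol section 2.2 says of grip strength: "The test will be conducted by either Drs. [name] or [name". Of Tinetti and of MOCA it says: "The test will be conducted by either Drs. [name] and [name". The names are removed in the public text, but in each case the tester is one of the study's doctors. No independent or masked assessor is mentioned.

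**When.** Section 2.2 ties the second test to sodium: "The test will be performed at baseline and 24 to 48 hours after correction of hyponatremia". Section 3.3 c) repeats the link: "Upon correction of hyponatremia these measurements will be repeated". Appendix 1 labels the second visit by corrected sodium.

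**Who learns the sodium and enrols.** Under section 3.2 the laboratory "will notify the study team (Drs. [name] and [name]) responsible for patient enrollment using a dedicated pager". Explaining the aims, taking consent and enrolling the patient all fall to someone from that same team.

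**Who handles the scores.** Section 7.1: "All data handling will be undertaken directly by the investigators". Section 7.2 has the investigators copy the paper forms into the data file.

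**What is tested.** Section 2.1 states a directional hypothesis: strength, balance and cognition improve once sodium is corrected. Section 4.1 compares each patient only with himself or herself, by Wilcoxon signed-rank test at p ≤ 0.05.

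No section masks the tester to visit or sodium, withholds visit 1 scores at visit 2, or provides a second scoring. The coding in section 7.3 protects patient identity and does not mask the assessor.

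**The concern.** In this design the sodium state, the order of the visits and the tester's knowledge all change together, in the same direction for every patient. There is no comparison group in which the tester's expectation is the same but sodium is not corrected.

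If the tester rates a little more generously at visit 2, or encourages the patient more, the extra points enter the before/after difference exactly as true recovery would. A visit 1 sheet within view adds an anchor. The Wilcoxon test cannot tell these sources apart, and no covariate could be added later to do so.

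Tinetti is the test for which the protocol itself describes graded rating by the observer (0 to 2 per item). For MOCA and grip, scope for judgement or encouragement is a reasonable expectation, but the text supplied does not document it.

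Who scores, and what the scorer may see, belongs to the conduct of the study. Section 2.2 already names the testers, so this is not a detail waiting for an analysis plan.

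**Working it through.** **Step 1: is any tester masked?**

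| Question | Where | Answer |
|---|---|---|
| Who gives the tests? | 2.2 | Study doctors |
| What triggers visit 2? | 2.2, 3.3 c), Appendix 1 | Corrected sodium |
| Can the visit 2 tester be unaware of visit or sodium? | follows from the rows above | No |
| Are visit 1 scores withheld? | 2.2, 3.3, 7.1 to 7.3 | No rule |
| Is there a comparison group? | 4.1 | No, own baseline only |
| Predicted direction? | 2.1 | Improvement |

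The confounding follows from these rows whoever the individual doctors are.

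**Step 2: what the protocol's own figure says about the spread.** Section 3.1 gives 44 patients for a 5-point MOCA difference at 90% power and two-sided alpha 0.05, with 50 to be enrolled. It states no SD, so 44 cannot be reproduced from its inputs. Solving backwards with 1.960 + 1.282 = 3.242:

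- Paired reading: SD of change = 5 × √44 / 3.242 = 10.2 (10.0 with the t distribution).
- Two-sample reading with 22 per group: SD of the score = 5 / (3.242 × √(2/22)) = 5.1 (5.0 with the t distribution).

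The SD of the paired change is therefore an assumption, and I carry it across a range.

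**Step 3: how small a shift is enough?** With no true change, the observed mean change that just reaches p = 0.05 is about 1.96 × SD / √n. At n = 50:

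- SD 3: 1.96 × 3 / 7.071 = 0.83 points
- SD 4: 1.11 points
- SD 5: 1.39 points
- SD 10.2: about 2.8 points

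**Step 4: chance of a false improvement.** The normal approximation is Φ(b × √n / SD − 1.96), with b the mean scoring shift. For b = 1, SD 3, n = 50: Φ(2.357 − 1.96) = Φ(0.397) = 0.65. Simulation of the Wilcoxon signed-rank test (3,000 trials per cell for SD 3 and 4), no true change, n = 50:

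| SD of change (assumed) | Shift 0.5 | Shift 1: simulated | Shift 1: normal approx. |
|---|---|---|---|
| 3 | 20% | 61% | 65% |
| 4 | 14% | 40% | 42% |
| 5 | 10% | about 27% | 29% |
| 10.2 | 6% | about 10% | 10% |

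A repeat run gave 61%, 40%, 26% and 10% for the 1-point shift. With n = 44 and SD 10.2 the 1-point figure is 8% simulated and about 9.5% by the formula. With no shift, about 5% of trials reach p ≤ 0.05, half of them in the predicted direction.

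These figures show how sensitive the test is to a shift. They do not show that a shift occurs.

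**The case against.** **Same people in every role.** A reader might infer that those who are paged, enrol, test and handle the data are the same individuals. The matching two-doctor descriptions suggest it, but the names are removed and it cannot be confirmed. The point does not need it: no tester is masked, whoever that is.

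**Expectation always favours improvement.** A reader might also infer this from section 2.1. The preliminary studies in section 1, however, cite work finding no gait improvement after correction, no strength gain in moderate hyponatremia, and no link with mobility in heart failure. The stated hypothesis points one way, but expectation need not be equally strong for all three endpoints. The cited work favours it most clearly for cognition.

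**Grip is instrumental.** The dynamometer gives the reading and the best of three attempts is used, so lenient item scoring does not apply. Only encouragement could act, and the protocol fixes no wording for it.

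**The illustration is arbitrary.** Any systematic shift becomes significant at some sample size, and both the shift and the SD are assumed. That stands. The study is sized for 5 points, so 1 point is one fifth of the target difference. At larger SDs the effect is modest.

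**Masking is hardly possible.** In an unfunded, single-centre before/after study, unmasked testing is largely inherent. Rescoring reaches MOCA only in part and Tinetti not at all. This limits the remedy to reducing the bias and declaring it. It does not explain why visit 1 sheets are left open or instructions unscripted.

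**Conclusion.** The point holds as a design weakness. All three tests are given by unmasked study doctors, visit 2 is defined by corrected sodium, and visit 1 scores are not withheld. Rater expectation is therefore confounded with recovery and cannot be separated afterwards.

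The stronger reading, that expectation will produce the predicted gain, is not supported: the documents give no size for any leniency and no SD of change. Under the assumptions shown, a 1-point MOCA shift with no true effect would be declared significant in roughly one quarter to three fifths of trials for an SD of 3 to 5, and in about one tenth if the SD is near 10. The weakness is worth correcting because the useful steps are cheap beforehand and unavailable once the data are collected.

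**What to change.** Add to section 2.2:

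1. The visit 1 MOCA, Tinetti and grip sheets are sealed on completion and opened only when the visit 2 sheets are complete.
2. One fixed script of instructions and encouragement is used for all three tests at both visits.
3. A statement that assessors were unmasked to visit and sodium, and that expectation cannot be separated from recovery, especially for Tinetti.

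Optional, as a sensitivity analysis: record MOCA answers and drawings verbatim, and have an existing investigator who tested that patient at neither visit, where there is one, rescore the coded sheets in random order with date, visit and sodium removed.

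**Cost.** Items 1 to 3 need envelopes, a one-page script and minor handling, with no extra staff. The optional rescoring covers 50 × 2 = 100 sheets. At an assumed 5 minutes each that is 500 minutes, about 8 hours, plus time for coding and verbatim recording.

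**Downside.** The bias is reduced only in part. Sealing removes the anchor of the earlier sheet but not the tester's memory or knowledge of the visit, and rescoring cannot undo influence during administration.

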### 2.3 Project design

We will conduct a single-center, prospective, observational study at the General Hospital Solothurn. The study will be conducted at the Department of Emergency Medicine, where patients will be screened for hyponatremia, and the Department of General Internal Medicine, where screening will occur both in the inpatient and outpatient services.

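### The MOCA is repeated with one named form, in a fixed order and without a comparison group, so item learning cannot be separated from recovery after sodium correction

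*Protocol*

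**What the plan says.** Section 2.2 describes the MOCA material and timing: "The MOCA form is shown in the Appendix. The test will be performed at baseline and 24 to 48 hours after correction of hyponatremia". Section 3.3 c) says of the strength, Tinetti and MOCA measurements: "Upon correction of hyponatremia these measurements will be repeated". Appendix 1 lists a single MOCA line, ticked at both visits. No second version, practice session or group tested twice without correction is described.

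The design has one group (section 2.3): "We will conduct a single-center, prospective, observational study at the General Hospital Solothurn". Section 4.1 rests the comparison on pairing, because "samples will be dependent since every patient serves as his own control", and specifies the test: "Wilcoxon signed ranked tests will be used to compare results on muscle strength, Tinetti score and MOCA scores".

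Section 2.1 states what a change is meant to show. Aim C asks about "cognitive impairment that is reversible after correction of serum sodium", and the hypothesis is that "the correction of the serum sodium will lead to an improvement of these parameters". Section 3.1 sizes the study on the MOCA: 5 points, 90% power, two-sided alpha 0.05, 44 patients needed and 50 to be enrolled.

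**The concern.** A before/after change tested against zero contains everything that differs between the two sittings. One such difference is that at the second sitting the patient may have seen the items already. Because the order is always hyponatremic then corrected, any benefit of having seen them adds to the change in the hoped-for direction in every patient. With no comparison group there is nothing to subtract it with.

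At stake is aim C, on the endpoint that sets the sample size. If part of the MOCA change is item learning, a significant Wilcoxon result does not by itself show reversible impairment. This cannot be left to a later analysis document: once both visits have used the same items, the data hold no information that separates learning from recovery.

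**Working it through.** **Inputs from the protocol.** One MOCA form named, test repeated, fixed order (2.2, 3.3 c, Appendix 1); one group, paired Wilcoxon test, p ≤ 0.05 (2.3, 4.1); 5 points, 90% power, two-sided 0.05, n = 44, 50 to be enrolled (3.1).

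**Inputs not given, so assumed.** SD of the MOCA change: 3, 4, 5 or 10 points. Mean retest gain: 0, 0.5, 1 or 2 points. True sodium effect: zero.

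**Step 1: which SD fits the stated 44?** None is given, so it can only be solved backwards.
- Paired formula, n = (SD × (1.960 + 1.282) / 5)². With n = 44, SD = 5 × √44 / 3.242 = 10.2. The exact noncentral-t calculation gives 10.0.
- Unpaired formula, n per group = 2 × (SD × 3.242 / 5)². With SD = 5 this is 21.02, rounded up to 22 per group and 44 in total.

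So 44 fits an SD of change of about 10, or an SD of single scores of 5. In the second case the SD of change is 5 × √(2(1 − r)), where r is the correlation between the two scores: 5 if r = 0.5, and 3.2 if r = 0.8 (both values of r assumed). The range 3 to 10 therefore covers what the protocol's own figure allows under these readings.

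**Step 2: how often does a retest gain alone give p ≤ 0.05?** Two-sided Wilcoxon signed-rank test on 50 pairs, normal changes rounded to whole points, mean equal to the gain, 4,000 simulated studies per cell. Where two simulation runs differ, both figures are shown.

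| Assumed gain | SD 3 | SD 4 | SD 5 | SD 10 |
|---|---|---|---|---|
| 0 | 4.5% | 3.9% | 5.1% | 4.5% |
| 0.5 point | 20 to 21% | 13% | 11% | 7% |
| 1 point | 62% | 39 to 40% | 26 to 28% | 10% |
| 2 points | over 99% | 92 to 93% | 78 to 79% | 28% |

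**Step 3: check by formula.** For a paired t test the noncentrality is gain / SD × √50. At a gain of 1 it is 2.36, 1.77, 1.41 and 0.71 for SD 3, 4, 5 and 10. The chance of a significant improvement is then 64%, 41%, 28% and 10%. At a gain of 2 it is over 99%, 93%, 79% and 28%. These agree with the simulation.

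**Step 4: compare with the 5-point target.** The smallest mean change that reaches p ≤ 0.05 in a paired t test is about 2.01 × SD / √50 = 0.284 × SD. That is 0.9, 1.1, 1.4 and 2.8 points for SD 3, 4, 5 and 10. The significance threshold thus lies well below 5 points, which leaves room for a small retest gain to cross it. The assumed gains of 1 and 2 points are 20% and 40% of the target, so they would not by themselves look like a change of the planned size.

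**The case against.** **Reuse of the same items is not stated outright.** This stands. Section 2.2 uses the same sentence about a form for the Tinetti test, so the singular may simply name the instrument. The form itself is not in the text available, which is not held against the plan. A reader might infer that the protocol prescribes an identical form; it does not say so. Reuse is the natural reading, because one form is named, the measurement is said to be repeated and no second version appears. If two versions are intended, the protocol still needs a sentence to say it.

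**The interval may be long.** This stands too. A reader might infer that the sittings are only days apart. But the "24 to 48 hours after correction of hyponatremia" run from correction, not from baseline. Time to correction is not bounded, and section 2.3 includes outpatients. A longer gap may weaken item learning, but does not reverse its direction.

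**Learning is not shown to occur.** The documents give no retest gain for any population, least of all for patients first tested while hyponatremic. A reader might infer that learning will be counted as recovery. The documents support only that the two cannot be separated.

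**The remedy is partial.** Different items do not remove general test familiarity or recovery from the acute illness. Versions may differ in difficulty, and alternation need not balance exactly among completers, because drop-outs are replaced (3.4) and incomplete pairs are left out (4.2). This limits the benefit but does not remove it.

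**Conclusion.** The point holds in a limited form. As written, the plan gives no means of separating item learning from reversal of impairment on the MOCA, and any learning favours the hypothesis. If a retest gain exists, the Wilcoxon test does not keep its 5% level as a test of a sodium effect. For an assumed 1-point gain the rate is about 62% at SD 3 and 10% at SD 10; for 2 points it is over 99% and 28%. Gain and SD are both assumptions, and the lowest figures belong to the SD that fits n = 44 under a paired formula.

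A reader might go further and infer that a result of the planned size could arise from repetition alone. The figures do not support that: the gains examined are at most 2 points against a target of 5. The weakness lies in reading a significant p-value as reversal, not in a change near 5 points. The change to the plan should still be made before testing starts, because it is cheap and cannot be made afterwards.

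**What to change.** In section 2.2, state that different parallel versions of the MOCA, with different items, are used at the two visits, and that the version given first alternates with enrolment number (odd or even). Add a CRF field for the version used at each visit, and report how many analysed patients had each order.

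The cost is a second form and one field per visit, with no extra patient, visit or blood sample. There is a small loss of precision. If the versions differ in difficulty by an assumed 1 point, each patient's change shifts by +1 or −1; with equal numbers, an SD of change of 4 becomes √(16 + 1) = 4.1. If completers split 28 to 22, the remaining bias is (28 − 22) / 50 × 1 = 0.12 point. So alternation balances difficulty approximately, not exactly.

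The protocol does not say whether a parallel version exists in the study language. If none does, state this, do not interpret a significant MOCA gain as reversed impairment on the p-value alone, and report the size of the gain against the 5-point target. With either option, name general test familiarity and recovery from the acute illness as remaining explanations of a before/after change.
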